6.8. Concomitant Therapy

Medications will be classified into anatomical therapeutic chemical (ATC) drug classes using the latest version of the World Health Organization (WHO) Drug Dictionary. Medication start and stop dates will be compared to the date of first dose of treatment in Study AMAH to allow medications to be classified as concomitant for each treatment period.

Prior medications are those medications that start and stop prior to the date of first dose of study treatment. *Concomitant medications* are those medications that start before, on, or after the first day of study treatment of the defined treatment period and continue into the treatment period. For the ITT population, prior and concomitant medications will be summarized separately by preferred term in descending frequency. Additional summaries will be given for the use of (1) topical therapies, (2) topical steroid therapy, and (3) systemic corticosteroid therapy as concomitant therapies. The drugs included in these classes are defined by compound level safety standards.

6.9. Efficacy Analyses

[Table AMAH.6.3](#) includes the description and derivation of the efficacy/health outcomes measures and endpoints.

[Table AMAH.6.4](#) provides the detailed analyses including analysis type, method and imputation, population, and time point for efficacy/health outcomes analyses.

Table AMAH.6.3. Description and Derivation of Efficacy/Health Outcomes Measures and Endpoints

Measure	Description	Variable	Derivation/Comment	Definition of Missing/duplicate Components
sPGA	Static Physician Global Assessment (sPGA): the physician's global assessment of the patient's psoriasis lesions at a given time point. Plaques are assessed for induration, erythema, and scaling, and an overall rating of psoriasis severity is given using the anchors of: clear (0), minimal (1), mild (2), moderate (3), severe (4), or very severe (5).	sPGA score	Range from 0 to 5: clear (0), minimal (1), mild (2), moderate (3), severe (4), or very severe (5).	Single item, missing if missing. For the duplicate individual score at the same visit, choose the latest results.
		sPGA (0,1)	An sPGA assessed as either 0 or 1 with at least a 2-point improvement from baseline, which represents a clinically meaningful response of minimal plaque severity or complete resolution of plaque psoriasis.	Missing if sPGA is missing.
		sPGA (0)	An sPGA assessed as 0 with at least a 2-point improvement from baseline, which represents a clinically important endpoint indicating complete resolution of plaque psoriasis.	Missing if sPGA is missing.
PASI	Psoriasis Area and Severity Index (PASI): combines assessments of the extent of body-surface involvement in 4 anatomical regions (head and neck, trunk, arms, and legs) and the severity of scaling (S), redness (R), and plaque induration/infiltration (thickness, T) in each region, yielding an overall score of 0 for no psoriasis to 72 for the most severe disease (Fredriksson and Pettersson 1978).	PASI score	The composite PASI score is calculated by multiplying the sum of the individual-severity scores for each area by the weighted area-of-involvement score for that respective area, and then summing the 4 resulting quantities as follows: $\text{PASI} = 0.1(R_h + T_h + S_h)A_h + 0.2(R_u + T_u + S_u)A_u + 0.3(R_t + T_t + S_t)A_t + 0.4(R_l + T_l + S_l)A_l$ Where, R_h, R_u, R_t, R_l = redness score of plaques on the head, upper limb, trunk, and lower	If any individual score is missing, the PASI score will not be calculated, hence, missing.

Measure	Description	Variable	Derivation/Comment	Definition of Missing/duplicate Components
	
Severity is rated for each index (R, S, T) on a 0-4 scale (0 for no involvement up to 4 for very severe involvement):
 
0 = none 1 = slight 2 = moderate 3 = severe 4 = very severe
 
The body is divided into 4 anatomical regions comprising the head (h), upper limb (u), trunk (t), and lower limb (l). In each of these areas, the fraction of total body surface area affected is graded on a 0-6 scale (0 for no involvement; up to 6 for 90% - 100% involvement):
 
0 = 0% (clear) 1 = >0% to <10% 2 = 10% to <30% 3 = 30% to <50% 4 = 50% to <70% 5 = 70% to <90% 6 = 90% to 100%
 
The various body regions are weighted to reflect their respective proportion of body surface area.
		
limb, scored 0-4 respectively;
 
T_h, T_u, T_t, T_l = thickness score of plaques on the head, upper limb, trunk, and lower limb, scored 0-4 respectively;
 
S_h, S_u, S_t, S_l = scaliness score of plaques on the head, upper limb, trunk, and lower limb, scored 0-4 respectively;
 
A_h, A_u, A_t, A_l = numerical value translation of % area of psoriatic involvement score for the head, upper limb, trunk, and lower limb, respectively.
 
PASI scores are treated as a continuous score, with 0.1 increments within these values.
	
		PASI change from baseline	Calculated as: observed PASI – baseline PASI.	Missing if baseline or observed value is missing.
		PASI percent improvement from baseline	
Calculated as:
 $\text{Percent improvement from baseline} = 100 \times \frac{\text{Baseline PASI} - \text{Observed PASI}}{\text{Baseline PASI}}$ 
If a patient has experienced an improvement, this measure will be positive. If a patient has experienced a worsening in the condition, this measure will be negative.
	Missing if baseline or observed value is missing.
PASI 75	A clinically meaningful response; ≥75% improvement in PASI score from baseline.	Missing if baseline or observed value is missing.		

Measure	Description	Variable	Derivation/Comment	Definition of Missing/duplicate Components
		PASI 90	Higher level of clearance; PASI 90 is a $\geq 90\%$ improvement in PASI score from baseline.	Missing if baseline or observed value is missing.
		PASI 100	Complete resolution of plaque psoriasis; a 100% improvement in PASI score from baseline.	Missing if baseline or observed value is missing.
PSS	
The Psoriasis Symptoms Scale (PSS) is a patient-administered assessment of 8 symptoms: itch, pain, discomfort, stinging, burning, redness, scaling, and cracking. Respondents are asked to answer the questions based on their psoriasis symptoms. The overall severity for each individual symptom from patient’s psoriasis is indicated by selecting the number from an NRS of 0 to 10 that best describes the worst level of each symptom in the area in the past 24 hours, where 0 (= no severity) and 10 (worst imaginable severity). The symptom severity scores, ranging from 0 to 10, are the values of the selected numbers indicated by the patient on the instrument’s horizontal scale. Each of the 8 individual items will receive a score of 0 to 10 and will be reported as item scores for itch, pain, discomfort, stinging,
	PSS item scores	The PSS score for each item as collected during office based assessment. itch, pain, discomfort, stinging, burning, redness, scaling, and cracking	The item is missing if it is not present in the data.
		PSS symptoms score	Calculated by summing the individual item scores as follows: itch NRS + pain NRS + stinging NRS + burning NRS.	If any of the 4 relevant item scores are missing, the score is missing.
		PSS signs score	Calculated by summing the individual item scores as follows: redness NRS + scaling NRS + cracking NRS	If any of the 3 relevant item scores are missing, the score is missing.
		PSS symptoms score of 0	Free of itch, pain, stinging, and burning.	Missing if PSS symptoms score is missing.
		PSS signs score of 0	Free of redness, scaling, and cracking	Missing if PSS signs score is missing.
		PSS symptoms, signs score change from baseline	Change from baseline = Observed PSS score – Baseline PSS score. Here “PSS score” could refer to the items, symptoms or signs score. Negative change indicates improvement and a positive change indicates deterioration of the condition.	Missing if either observed or baseline PSS score is missing.

Measure	Description	Variable	Derivation/Comment	Definition of Missing/duplicate Components
	burning, redness, scaling, and cracking.			
PSSI	
Psoriasis Scalp Severity Index (PSSI): in patients with scalp psoriasis at baseline. The scalp will be assessed for erythema (redness), induration (hardness), and desquamation (shedding of skin) and percentage of area affected as follows: Erythema, Induration, and Desquamation: 0 = Absent 1 = Slight 2 = Moderate 3 = Severe 4 = Severest Possible Percent of Scalp Involved: 0 = none 1 = <10% 2 = 10 – 29% 3 = 30 – 49% 4 = 50 – 69% 5 = 70 – 89% 6 = 90 – 100%
	PSSI score	The PSSI score is a composite score derived from the sum of the scores for erythema, induration and desquamation multiplied by the score for the extent of scalp area involved (percent of scalp involved). The range is 0 to 72.	If any individual score is missing, the PSSI score will not be calculated, hence missing. For the duplicate individual score at the same visit, choose the latest results.
		PSSI score change from baseline	Calculated as: observed PSSI – baseline PSSI	Missing if baseline or observed value is missing.
		PSSI score = 0	A PSSI assessed as 0, which represents the absence of scalp psoriasis.	Missing if PSSI score is missing.
NAPSI	Nail Psoriasis Severity Index (NAPSI): in patients with fingernail psoriasis involvement at baseline, NAPSI will be used to evaluate the severity of fingernail bed psoriasis and fingernail matrix psoriasis by area of involvement in the fingernail unit. The	NAPSI score	The NAPSI score of a fingernail is the sum of scores in fingernail bed and fingernail matrix from each quadrant (maximum of 8). Each fingernail is evaluated, and the sum of all the fingernails is the total NAPSI score (range 0 to 80), usually indicated as NAPSI score.	For each fingernail, if either bed or matrix score is missing or not done, the score for that finger is missing. If <50% of the finger scores from 10 fingers are missing, the

Measure	Description	Variable	Derivation/Comment	Definition of Missing/duplicate Components
	
finger nail is divided with imaginary horizontal and longitudinal lines into quadrants. Each fingernail is given a score for fingernail bed psoriasis (0 to 4) and fingernail matrix psoriasis (0 to 4), depending on the presence (score of 1) or absence (score of 0) of any of the features of fingernail bed and fingernail matrix psoriasis in each quadrant:
 
0 = None 1 = present in one quadrant of nail 2 = present in two quadrants of nail 3 = present in three quadrants of nail 4 = present in four quadrants of nail
			
imputation will be performed by using the average score of the remaining fingernails. If $\geq 50\%$ of the finger scores are missing, the NAPSI score will be left as missing. For the duplicate scores at the same visit, choose the latest results

		NAPSI score change from baseline	Calculated as: observed NAPSI – baseline NAPSI	Missing if baseline or observed value is missing.
		NAPSI score = 0	A NAPSI assessed as 0, which represents the absence of nail psoriasis.	Missing if NAPSI score is missing.

Measure	Description	Variable	Derivation/Comment	Definition of Missing/duplicate Components
PPASI	
Palmoplantar Psoriasis Area and Severity Index (PPASI): in patients with palmoplantar psoriasis at baseline, both palms and soles on each hand and foot will be individually assessed for erythema, induration, desquamation and percentage of area affected as follows: Erythema (E), Induration (I), and Desquamation (D): 0 = None 1 = Slight 2 = Moderate 3 = Severe 4 = Very Severe Percent of Palm and Sole Area Covered: 0 = None 1 = <10% 2 = 10 – 29% 3 = 30 – 49% 4 = 50 – 69% 5 = 70 – 89% 6 = 90 – 100%
	PPASI score	
The PPASI score is a composite score derived from the sum scores for erythema, induration, and desquamation multiplied by a score for the extent of palm and sole area involvement. The range is 0 to 72. $PPASI = 0.2(E_{rp} + I_{rp} + D_{rp})A_{rp} + 0.2(E_{lp} + I_{lp} + D_{lp})A_{lp} + 0.3(E_{rs} + I_{rs} + D_{rs})A_{rs} + 0.3(E_{ls} + I_{ls} + D_{ls})A_{ls}$ where: $E_{rp}, E_{lp}, E_{rs}, E_{ls}$ = Erythema score of plaques on the right palm (rp), left palm (lp), right sole (rs), left sole (ls), scored 0-4 respectively; $I_{rp}, I_{lp}, I_{rs}, I_{ls}$ = Induration score of plaques on the right palm (rp), left palm (lp), right sole (rs), left sole (ls), scored 0-4 respectively; $D_{rp}, D_{lp}, D_{rs}, D_{ls}$ = Desquamation score of plaques on the right palm (rp), left palm (lp), right sole (rs), left sole (ls), scored 0-4 respectively; $A_{rp}, A_{lp}, A_{rs}, A_{ls}$ = numerical value translation of % area covered for the right palm, left palm, right sole, and left sole, respectively.
	
If any individual score is missing, the PPASI score will not be calculated, hence, missing. For the duplicate scores at the same visit, choose the latest results.

		PPASI change from baseline	Calculated as: observed PPASI – baseline PPASI.	Missing if baseline or observed value is missing.

Measure	Description	Variable	Derivation/Comment	Definition of Missing/duplicate Components
		PPASI percent improvement from baseline	Calculated as: $\text{Percent improvement from baseline} = 100 \times \frac{\text{Baseline PPASI} - \text{Observed PPASI}}{\text{Baseline PPASI}}$ If a patient has experienced an improvement, this measure will be positive. If a patient has experienced a worsening in the condition, this measure will be negative.	Missing if baseline or observed value is missing.
		PPASI 50	A \geq 50% improvement in PPASI score from baseline	Missing if baseline or observed value is missing.
		PPASI 75	A \geq 75% improvement in PPASI score from baseline	Missing if baseline or observed value is missing.

Measure	Description	Variable	Derivation/Comment	Definition of Missing/duplicate Components
		PPASI 100	a 100% improvement in PPASI score from baseline	Missing if baseline or observed value is missing.
DLQI	Dermatology Life Quality Index (DLQI): is a validated, dermatology-specific, patient-reported measure that evaluates patient’s health-related QoL. This questionnaire has 10 items that are grouped in 6 domains, including symptoms and feelings, daily activities, leisure, work and school, personal relationships, and treatment. The recall period of this scale is over the “last week.” Response categories and corresponding scores are: Very much = 3 A lot = 2 A little = 1 Not at all = 0 Not relevant = 0	DLQI total score	A DLQI total score is calculated by summing all 10 question responses, and has a range of 0 to 30 (less to more impairment) (Finlay and Khan 1994; Basra et al. 2008).	If 2 or more questions are missing, the total score is missing. Note: #7B could be a valid missing while #7A is not “No.” That is, #7 should be considered as 1 question.
		DLQI (0,1)	A DLQI (0,1) response is defined as a post-baseline DLQI total score of 0 or 1. A DLQI total score of 0 to 1 is considered as having no effect on a patient’s HRQoL (Khilji et al. 2002; Hongbo et al. 2005).	Missing if DLQI total score is missing.
		DLQI (0,1) and DLQI total score ≥ 5 improvement from baseline	Patient is a DLQI (0,1) responder and reduction/decrease of ≥ 5 points from baseline	Missing if baseline or the total score is missing.

Abbreviations: DLQI = Global Assessment Dermatology Life Quality Index; HRQoL = health-related quality of life; NRS = Numeric Rating Scales; SAP = statistical analysis plan; PASI = Psoriasis Area and Severity Index; PSS = Psoriasis Symptoms Scale; PSSI = Psoriasis Scalp Severity Index; sPGA = Static Physician Global Assessment.

Table AMAH.6.4. Description of Efficacy/Health Outcomes Analyses

Measure	Variable	Analysis Method (Section 6.1.3)	Population (Section 6.1.1)	Time Point
PASI	PASI 90 (Primary)	Descriptive analysis with Observed, NRI, mNRI and Multiple Imputation	ITT - patients who entered Study AMAH with a PASI 90 response	All visits in corresponding Periods
	PASI 75; PASI 90; PASI 100 (Secondary)	Descriptive analysis with Observed, NRI, mNRI and Multiple Imputation	ITT	All visits in corresponding periods
sPGA	sPGA (0,1) (Primary)	Descriptive analysis with Observed, NRI, mNRI and Multiple Imputation	ITT - patients who entered Study AMAH with sPGA (0,1)	All visits in corresponding periods
	sPGA (0); sPGA (0,1) (Secondary)	Descriptive analysis with Observed, NRI, mNRI and Multiple Imputation	ITT	All visits in corresponding periods
PSS	PSS symptoms score of 0;	Descriptive analysis with Observed, NRI, mNRI and Multiple Imputation	ITT – patients with a PSS symptoms score ≥ 1 at Baseline	All visits in corresponding periods
	PSS signs score of 0;	Descriptive analysis with Observed, NRI, mNRI and Multiple Imputation	ITT – patients with a PSS signs score ≥ 1 at Baseline	All visits in corresponding periods
PSSI	PSSI change from baseline	Descriptive analysis with Observed and Multiple Imputation	ITT - patients with Scalp Involvement at Baseline	All visits in corresponding periods
	PSSI = 0	Descriptive analysis with Observed, NRI, mNRI and Multiple Imputation	ITT – patients with Scalp Involvement at Baseline	All visits in corresponding periods
PPASI	PPASI change from baseline	Descriptive analysis with Observed and Multiple Imputation	ITT - patients with Palmoplantar Involvement at Baseline	All visits in corresponding periods

Measure	Variable	Analysis Method (Section 6.1.3)	Population (Section 6.1.1)	Time Point
	PPASI 50; PPASI 75; PPASI 100	Descriptive analysis with Observed, NRI, mNRI and Multiple Imputation	ITT – patients with Palmoplantar Involvement at Baseline	All visits in corresponding periods
NAPSI	NAPSI change from baseline	Descriptive analysis with Observed and Multiple Imputation	ITT - patients with Nail Psoriasis Involvement at Baseline	All visits in corresponding periods
	NAPSI = 0	Descriptive analysis with Observed, NRI, mNRI and Multiple Imputation	ITT – patients with Nail Psoriasis Involvement at Baseline	All visits in corresponding periods
DLQI	DLQI (0,1)	Descriptive analysis with Observed, NRI, mNRI and Multiple Imputation	ITT - patients with Baseline DLQI > 1	All visits in corresponding periods
	DLQI (0,1) and ≥5-point reduction from Baseline	Descriptive analysis with Observed, NRI, mNRI and Multiple Imputation	ITT – patients with DLQI ≥5 at Baseline	All visits in corresponding periods

Abbreviations: DLQI = Global Assessment Dermatology Life Quality Index; mNRI = modified non responder imputation; NAPSI = Nail Psoriasis Severity Index; PASI = Psoriasis Area and Severity Index; PASI 75/90/100 = ≥75%/90%/100% improvement from baseline in the Psoriasis Area and Severity Index; PPASI = Palmoplantar Psoriasis Severity Index; PPASI 50/75/100 = ≥50%/75%/100% improvement from baseline in the Palmoplantar Psoriasis Severity Index; PSS = Psoriasis Symptoms Scale; PSSI = Psoriasis Scalp Severity Index; sPGA = Static Physician Global Assessment.

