6.3.3. Non-Responder Imputation

The non-responder imputation (NRI) method will be used to implement the composite strategy [ICH E9(R1)] for handling intercurrent events. This strategy is used to assess the combination of the effect of the study treatment with the occurrence of an intercurrent event. In this strategy patients are defined as responders only if they meet the clinical requirements for response at the predefined time AND they remain on the assigned study treatment. Failing either criteria by definition makes them nonresponders.

Patients will be considered non-responders for the NRI analysis if they do not meet the clinical response criteria or have missing clinical response data at the analysis time point. Enrolled patients without at least 1 observation within Study AMAH will also be defined as nonresponders for the NRI analysis. Analysis of binary categorical efficacy and health outcome variables may be assessed using an NRI method.

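### The missing-item rule for PASI, PSSI and PPASI makes no exception for a region with area score 0, so a score that the formula fully determines can be set to missing

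*SAP*

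**What the plan says.** In the last column of SAP Table AMAH.6.3 (Section 6.9), the rule for PASI is "If any individual score is missing, the PASI score will not be calculated, hence, missing". PSSI has "If any individual score is missing, the PSSI score will not be calculated, hence missing" and PPASI has "If any individual score is missing, the PPASI score will not be calculated, hence, missing". None of the three makes an exception for a clear region.

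The same table defines each score as a product. PASI is obtained by "multiplying the sum of the individual-severity scores for each area by the weighted area-of-involvement score for that respective area" and adding the four regions, with area graded "0 for no involvement; up to 6 for 90% - 100% involvement". PSSI is "the sum of the scores for erythema, induration and desquamation multiplied by the score for the extent of scalp area involved". PPASI is built from "sum scores for erythema, induration, and desquamation multiplied by a score for the extent of palm and sole area involvement", over two palms and two soles. For PSSI and PPASI too, 0 is an allowed area grade.

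Missingness carries forward. PASI 75/90/100 and PPASI 50/75/100 are missing when the observed score is missing, and PSSI = 0 is missing when PSSI is missing. Under SAP Section 6.3.3, NRI makes patients non-responders "if they do not meet the clinical response criteria or have missing clinical response data at the analysis time point". Protocol Section 10.3.1.1 names NRI as the primary method for binary efficacy endpoints. SAP Sections 6.1.3 and 6.3.4 make mNRI primary and NRI secondary.

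**The concern.** The rule treats every blank item as lost information. That is right where the region is involved. It is not right where the area score is 0, because the blank item is then multiplied by 0.

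The severity items grade plaques, and a clear region has none, so blanks in clear regions are conceivable. They would arise mainly in clear or nearly clear patients, so any loss would depend on outcome. PASI 90 among patients who entered with a PASI 90 response is one of the two primary endpoints. PASI 100 is a protocol secondary endpoint, and PSSI = 0 and PPASI 100 are further SAP endpoints; all three require an exact zero. A blank at Visit 1 could also leave a patient's entry PASI 90 status, and so membership of the primary set, undetermined.

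**Working it through.** **Inputs from SAP Table AMAH.6.3.** PASI weights: head 0.1, upper limb 0.2, trunk 0.3, lower limb 0.4. PPASI weights: 0.2 for each palm, 0.3 for each sole. PSSI has one region. Each of three severity items runs 0 to 4, and area runs 0 to 6. **Not in the documents (assumed below):** baseline PASI, the true response rate, and the frequency of blank items.

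**1. Reproduce the stated range.** The maximum severity sum is 3 × 4 = 12.
- PASI: (0.1 + 0.2 + 0.3 + 0.4) × 12 × 6 = 72.
- PPASI: (0.2 + 0.2 + 0.3 + 0.3) × 12 × 6 = 72.
- PSSI: 12 × 6 = 72.

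All three match the SAP's range of 0 to 72.

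**2. Area score 0.** A region's contribution is w × (R + T + S) × A. With A = 0, all 5 × 5 × 5 = 125 severity combinations give 0 in every PASI region. The same product form gives 0 for PSSI and for each PPASI region. Likewise, if all three severity items are 0, the contribution is 0 for any area grade.

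**3. Where the rule is justified.** With A = 1 and one severity item missing, the contribution is uncertain by w × 4 × 1: 0.4 points for the head, 0.8 for the upper limb, 1.2 for the trunk and 1.6 for the lower limb. Setting the total to missing is defensible there.

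**4. Two patients with blank severity items in clear regions only.**
- All four areas 0: PASI = 0, a PASI 100 response.
- Lower limb A = 1 with R = T = S = 1, other areas 0: PASI = 0.4 × 3 × 1 = 1.2. From assumed baselines of 12, 15 and 20, the improvement is 10.8/12 = 90%, 13.8/15 = 92% and 18.8/20 = 94%, a PASI 90 response in each case.

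Under the rule as written, both scores are missing.

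**5. Follow the missing score through each analysis.**
- *NRI (SAP 6.3.3):* both patients are non-responders at that visit.
- *mNRI (SAP 6.3.4):* non-response is imposed only for discontinuation because of an adverse event (including death) or lack of efficacy. An isolated gap therefore falls to MI.
- *MI (SAP 6.3.2):* an intermittent gap is filled from a multivariate normal model. Such a draw is almost never exactly 0, and no rounding or truncation rule is given. How the draw would count towards PASI 100, PPASI 100 or PSSI = 0 is therefore unspecified. A gap with no later observed score would go to predictive mean matching, which can return an observed 0.
- *As observed (SAP 6.3.1):* the visit drops out.
- *sPGA (0,1):* a single item, unaffected.

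**6. Illustrative size under NRI.** Let p be the true response rate and q the share of true responders whose score is lost in this way. The reported rate is p × (1 − q).

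| Assumed q | p = 90% | p = 80% |
|---|---|---|
| 1% | 89.1% | 79.2% |
| 3% | 87.3% | 77.6% |
| 5% | 85.5% | 76.0% |

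At p = 90% the losses are 0.9, 2.7 and 4.5 percentage points.

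**The case against.** The strongest reply is that the trigger may never occur. All three severity scales have a 0 code for none or absent, so a clear region can be recorded completely. Protocol Appendix 3.2 commits the sponsor to computer edits, source checks and a database quality review, and Appendix 3.2.1 allows electronic capture of scales. Entry rules usually sit in data-capture specifications that are not part of these documents. All of this stands. The effect is nil if assessors enter the 0, if the device forces an entry, or if blanks are queried and completed. A reader might infer that only a forced entry would remove it; that is too strong.

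A reader might also infer that clear patients become failures in the primary analysis. That holds for NRI, which the protocol calls primary, but not for the SAP's mNRI. No downward bias in PASI 90 has been shown under mNRI, MI or observed data. Because the SAP reports all four methods by visit, a large NRI artefact should show as a gap between them.

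Requiring complete components is a transparent convention, applied alike to every cohort in a study without hypothesis tests. The SAP does rescue partly missing NAPSI (averaging the remaining fingernails when fewer than half are missing) and DLQI (one missing question tolerated). That contrast does not by itself make the PASI rule an error.

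Lastly, an unconditional rule that area 0 means a contribution of 0 would settle contradictory records, such as area 0 with redness 2 and thickness blank, in favour of response. This is a fair point, and the fix allows for it.

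None of this changes the algebra: the written rule can discard a score that its own formula determines.

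**Conclusion.** The gap is real and follows from the SAP's text alone: no area-0 exception exists for PASI, PSSI or PPASI, although the contribution is then exactly 0. Its practical size is unknown, because it depends on how often severity items are left blank in clear regions and neither document gives that. The percentage-point losses above show scale at assumed rates; they are not estimates for this trial. The documents do not support a claim that PASI 90 or PASI 100 will be understated, nor a stated share of entry responders with fully clear regions. Among the primary endpoints only PASI 90 is exposed. If an area score is missing and any severity item is above 0 or blank, the contribution is generally unknown and the present rule is right. Overall the point is of minor-to-moderate importance and costs almost nothing to correct.

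**What to change.** In the missing-components column of SAP Table AMAH.6.3, for PASI, PSSI and PPASI, state:

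- A region contributes 0, even with items blank, if its area score is 0 and no recorded severity score there is above 0.
- A region also contributes 0 if all three severity scores are 0 and the area score is missing.
- Conflicting entries (area 0 with a recorded severity above 0) are queried.
- In every other case a missing item leaves the total missing, as now.

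For PSSI the region is the scalp; for PPASI it is each palm or sole.

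The cost is a sentence or two of SAP text, a small change to the derivation code and one edit check. The change adds no assumption beyond the SAP's own formula and alters no score if no such blanks occur. Reporting how many scores it recovers would settle how much the point mattered.

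### A fingernail with a recorded positive bed or matrix score can be dropped and refilled as 0, so NAPSI = 0 can be credited to a patient whose record shows nail psoriasis

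*SAP*

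**What the plan says.** The NAPSI rows of SAP Table AMAH.6.3 (Section 6.9) build the score in three steps.

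- **Nail level.** Bed and matrix are each scored 0 to 4, so a nail scores 0 to 8 and ten nails 0 to 80. On incomplete nails: "For each fingernail, if either bed or matrix score is missing or not done, the score for that finger is missing". The half that was recorded is not used.
- **Total.** "If <50% of the finger scores from 10 fingers are missing, the" "imputation will be performed by using the average score of the remaining fingernails". At 50% or more "of the finger scores are missing, the NAPSI score will be left as missing".
- **Clearance.** The variable NAPSI score = 0 is defined as "A NAPSI assessed as 0, which represents the absence of nail psoriasis", and its missing-data entry reads "Missing if NAPSI score is missing".

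Table AMAH.6.4 analyses NAPSI = 0 at all visits by Observed, NRI, mNRI and MI, in patients with nail involvement at baseline. Protocol Section 9.1.2.4 has every fingernail evaluated and gives no rule for incomplete nails.

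**The concern.** Filling a few nails with the mean of the rest is a common and reasonable way to rescue a total score. It suits a clearance endpoint less well, because clearance depends on whether any disease is present and not on the average amount.

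The half-score rule goes a step further. It discards a score that was actually recorded, and that score may be the only evidence of disease at the visit. The patient is then reported as free of nail psoriasis although the case report form shows otherwise, which contradicts the SAP's own description of the variable. No clause keeps a positive half-score or bars a prorated 0 from counting as clearance.

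In the same table PASI, PSSI and PPASI are not calculated when any component is missing. PSSI = 0, the parallel scalp variable, therefore cannot be reached with an unscored component, but NAPSI = 0 can.

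**Working it through.** **Inputs** (SAP Table AMAH.6.3): bed 0–4; matrix 0–4; nail missing if either half is missing; proration if fewer than 5 of 10 nails are missing; response missing only if the total is missing.

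**Formula.** With k incomplete nails and k ≤ 4, total = S + k × S/(10 − k), where S is the sum over the complete nails. With k ≥ 5 the total is missing.

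**Check against the plan's own figure.** Ten nails at 4 + 4 give S = 80 and k = 0, so the total is 80. This matches the stated range of 0 to 80.

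**Records put through the rule**

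| Record | S | k | Total | NAPSI = 0? | Full total could be |
|---|---|---|---|---|---|
| Nine nails 0; tenth has bed 3, matrix not done | 0 | 1 | 0 + 1 × 0/9 = 0 | Yes | 3 to 7 |
| Six nails 0; four have bed 4, matrix not done | 0 | 4 | 0 + 4 × 0/6 = 0 | Yes | 16 to 32 |
| Six nails 0; four not assessed | 0 | 4 | 0 + 4 × 0/6 = 0 | Yes | 0 to 32 |
| Eight nails 0, one nail 1, one not assessed | 1 | 1 | 1 + 1 × 1/9 = 1.11 | No | 1 to 9 |
| Five nails 0; five not assessed | 0 | 5 | missing | missing | 0 to 40 |

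In the first two records the data already on file rule out a total of 0. In the third they do not.

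**Direction.** A truly clear patient has only zeros recorded, so S = 0 and the prorated total cannot be positive. A patient with disease gets 0 when one to four nails are incomplete and every complete nail scores 0. Proration can therefore produce false clearance but not false non-clearance.

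**Do the missing-data methods catch it?**

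- NRI (Section 6.3.3) acts when the criterion is not met or the response is missing. A prorated 0 meets the criterion and is not missing.
- mNRI (Section 6.3.4) acts on an unmet criterion or on data missing after discontinuation. Neither applies.
- MI (Section 6.3.2) imputes missing scores and, in step 4, derives the response from the completed continuous score. A total of 0 is already present, so it stays 0.
- Observed uses the total as it stands.

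All four methods count the first record as cleared.

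**Size, conditional only.** Suppose exactly one nail is affected and k of 10 nails are incomplete at random. The chance that the affected nail is among them is k/10: 10%, 20%, 30% and 40% for k = 1 to 4. With two affected nails the chance is C(k,2)/C(10,2): 0%, 2.2%, 6.7% and 13.3%. These figures cover every kind of incomplete nail, not just those with a positive half on record. They say nothing about how often k exceeds 0, which the documents do not give.

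**The case against.** **The endpoint is peripheral.** This stands. NAPSI = 0 was added in SAP Version 2 (Section 3). The listed secondary endpoint in SAP Table AMAH.4.1 is the change in NAPSI. Section 6.1 plans the listed endpoints for the study report and says additional efficacy results may be included. Section 6.4 rules out hypothesis testing.

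**The frequency may be close to nil.** This cannot be excluded. Protocol Appendix 3.2 describes computer edits and a database quality review, and the documents do not say whether half-scored nails are allowed or queried. A reader might assume that each of the 20 items is missing independently at 1%, 3% or 5%. With one affected nail that yields false clearance at about 2.0%, 5.9% and 9.7% of visits (the affected nail incomplete and no more than three others). But the same assumption makes 1 − (1 − p)^20 = 18%, 46% and 64% of nail assessments incomplete, which nothing in the documents supports. Those percentages should not be used as an estimate.

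**Overstatement under NRI.** A reader might infer that the reported NRI clearance rate is too high overall. That does not follow. NRI also counts truly clear patients as failures when they miss a visit, discontinue or have five or more nails unscored, so the net direction is undetermined.

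**Tolerance of missing items is not unique to NAPSI.** This is correct: the DLQI total in the same table allows one unanswered question and also feeds threshold endpoints. It does not meet the narrower point that a recorded positive nail score is thrown away.

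**The word assessed may imply observed values only.** The adjacent missing-data entry defeats that reading, since a prorated total is not a missing one.

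**Conclusion.** The point holds in a narrow form. As the SAP is written, a positive bed or matrix score can be on file at a visit while the patient is counted as having no nail psoriasis under all four analysis methods. This follows from the text alone and needs no assumption about rates. It requires one to four incomplete nails and zeros on every complete one.

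The size is unknown, because it depends on nail-level missingness and on how many patients have one or two affected nails, and the documents report neither. The one-way direction belongs to proration itself and not to the published clearance rate.

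A reader might also treat a wholly unassessed nail as the same error. It is a weaker case: the record then neither shows nor excludes disease, so how to handle it is an analysis choice to be tested by sensitivity analysis. No primary or listed secondary conclusion rests on NAPSI = 0, so this is a minor clarification worth making because it is nearly free.

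**What to change.** Add to the NAPSI = 0 row of Table AMAH.6.3: *NAPSI = 0 is not achieved at a visit if any bed or matrix score recorded at that visit is above 0, whatever the prorated total; this applies under Observed, NRI, mNRI and MI alike.* The rule must be applied after the response is derived, because MI would otherwise return clearance from the total of 0. Proration can stay for the total and its change from baseline. The first record above would then show a total of 0 without clearance, which deserves a table footnote.

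As a sensitivity check (Section 6.9.5 currently lists none), report Observed and NRI results with NAPSI = 0 counted only when all fingernails are fully scored. Partly scored all-zero records would be left out under Observed and be non-responses under NRI.

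Do not send those records to MI while the prorated total of 0 is kept, because step 4 of Section 6.3.2 would read the response straight back from that total. Setting the total to missing instead is no remedy: Section 6.3.2 fills intermittent gaps from a multivariate normal model and states no rounding, so an imputed value would almost never be exactly 0.

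The cost is one SAP sentence, a few lines of derivation code and possibly a slightly lower clearance rate. No new data are needed.
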